6.6 Criteria for Taking a Participant Off Study

6.6.1 Subject Withdrawal

Subjects have the right to withdraw from the study at any time and for any reason without prejudice to their future medical care by the physician or at the institution.

Subjects can decline to continue to receive study required treatment and/or other protocol required procedures at any time during the study but continue to participate in the study. This is referred to as partial withdrawal of consent.

If partial withdrawal of consent occurs, the investigator must discuss with the subject the appropriate process for discontinuation from protocol required therapies and must discuss options for continued participation, completion of procedures and the associated data collection as outlined in the SOA. The level of follow-up and method of communication should also be discussed between the research staff and the subject and documented in the source documents.

Withdrawal of full consent from a study means that the subject does not wish to receive further protocol required therapy or undergo procedures and the subject does not wish to continue further study follow-up. Subject data collected up to withdrawal of consent will be retained and included in the analysis of the study, and where permitted by local regulations, publicly available data (death records) can be included after withdrawal of consent. The investigator is to discuss with the subject appropriate procedures for withdrawal from the study.

As part of the study sites may be asked to conduct searches of public records, such as those establishing survival status, if available, to obtain survival data for any subject for whom the survival status is not known. Sites may be also asked to also retrieve autopsy reports to confirm status of disease at the time of death.

The investigator and/or sponsor can also decide to withdraw a subject from the investigational product and/or other protocol-required therapies, protocol procedures, or the study as a whole or at any time prior to study completion.

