9.7.5 Long-term Follow-up Period

All subjects who complete the study, and those who withdraw from the study after receiving RT for reasons other than death, will be asked to participate in the long-term follow-up portion of this study up to 12 months from CAR-T infusion, with a focus on long-term efficacy and safety. These patients will also have long-term follow-up as part of the FDA mandated CIBMTR CAR T cell therapy registry.

The following procedures will be completed for subjects who are enrolled at the time points of 6, 9, and 12 months following CAR-T infusion, as outlined in the SOA (Long-term Follow-up Period) Table 3:

- Physical exam
- CTCAE/PRO-CTCAE Surveys
- PET-CT/ Disease assessment at 6 and 12 months per standard of care
- Survival status
- Labs
 - CBC with differential
 - Cytokine levels
 - Lymphocyte subsets
 - Translational lab collection.
- Subsequent therapy for the treatment of NHL
- **Refer to Sections 8.4** for targeted adverse/serious adverse event reporting
 - Including neurological, hematological, infections, autoimmune disorders, and secondary malignancies
- Targeted concomitant medication documentation (for 12 months or until disease progression, whichever occurs first)
 - Including gammaglobulins, immunosuppressive drugs, anti-infectives, and vaccinations

Subjects may be contacted by telephone to confirm survival status and report targeted concomitant medication use.

If a subject progress in the LTFU phase, the subject will continue to be followed for survival status and subsequent therapy for the treatment of NHL. A translational lab sample and **serum (for cytokine evaluation)** should be collected at the time of progression as part of CAR T cell therapy protocol, prior to starting any subsequent anti-cancer therapy.

Should the subject fail to return to the clinic for a scheduled protocol specific visit, sites will need to make 2 attempts by a combination of telephone and mail to contact the subject. Sites must document both attempts to contact the subject. If a subject does not respond within 1 month after the second contact the subject will be considered lost to follow-up and no additional contact will be required.

As patients will be receiving commercial product, patients will also have long-term follow-up as part of FDA mandated CAR T cell therapy registry.

Table 2. Schedule of Assessments

Procedures	Screening	Enrollment & RT Planning	Radiotherapy		Post Radiotherapy Period			

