12.1 Study Endpoints

Primary Endpoint:

- Rate and severity of RT-related toxicity as per CTCAE v5.0 criteria during RT or within the first 30 days of completing RT.

Secondary Endpoints:

- **Duration of response (DOR):** Among subjects who experience an objective response, DOR is defined as the date of their first objective response (which is subsequently confirmed) to disease progression per Lugano criteria¹ or death regardless of cause. Subjects not meeting the criteria for progression or death by the analysis data cutoff date will be censored at their last evaluable disease assessment date and their response will be noted as ongoing.
- **Objective response rate (ORR) per IRRC:** ORR per IRRC is defined as the incidence of either a complete response or a partial response by Lugano criteria¹ as determined by the IRRC. All subjects that do not meet the criteria for an objective response by the analysis data cutoff date will be considered non-responders.
- **Progression-free Survival (PFS):** PFS is defined as the time from RT completion date to the date of disease progression per Lugano criteria¹ or death from any cause. Subjects not meeting the criteria for progression by the analysis data cutoff date will be censored at their last evaluable disease assessment date.

- **Overall survival (OS):** OS is defined as the time from RT completion to the date of death. Subjects who have not died by the analysis data cutoff date will be censored at their last contact date.

Exploratory Endpoints:

- Levels of anti-CD19 CAR T cells in blood
- Levels of cytokines in serum
- Incidence of anti-axicabtagene ciloleucel antibodies
- Investigation of potential biomarker development based on assessment of blood cells, tumor cells and the proposed actions of the investigational product.

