12.4 Analysis of Primary and Secondary Endpoints

Planned Method of Analysis

The primary analysis of all treated subjects will take place once they have had the opportunity to be followed for 6 months.

Descriptive analyses may occur at any time.

Objective Response Rate

The incidence of objective response and exact 2-sided 95% confidence intervals will be generated.

Duration of Response

The competing-risk analysis method ^{24,25} will be used to estimate the cumulative incidence of relapse. The cumulative incidence of relapse in the presence of non-disease related mortality (the competing risk) will be estimated along with 2-sided 95% confidence intervals at 3-month intervals.

Progression-free Survival

Kaplan-Meier estimates and 2-sided 95% confidence intervals will be generated for progression-free survival time. Estimates of the proportion of subjects alive and progression-free at 3-month intervals will be provided.

Overall Survival

Kaplan-Meier estimates and 2-sided 95% confidence intervals will be generated for OS. Estimates of the proportion of subjects alive at 3-month intervals will be provided.

Safety

Subject incidence rates of adverse events including all, serious, fatal, CTCAE version 5.0 Grade 3 or higher and treatment related AEs reported throughout the conduct of the study will be tabulated by preferred term and system organ class. Changes in laboratory values and vital signs will be summarized with descriptive statistics. The incidence of concomitant medications will be summarized.

Tables and/or narratives of deaths through the long-term follow-up and treatment related SAEs will be provided.

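### If public-record searches are used, OS counts later deaths but not later survival among lost or withdrawn subjects, which biases it slightly downward

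*Combined protocol and SAP*

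**What the plan says.** - **Event (12.1).** "OS is defined as the time from RT completion to the date of death". Nothing limits how the death is learned.
- **Censoring (12.1).** "Subjects who have not died by the analysis data cutoff date will be censored at their last contact date". The term is not defined, and is not equated with the last date known alive.
- **Searches (6.6.1).** For subjects of unknown status, "sites may be asked to conduct searches of public records", the purpose being "to obtain survival data for any subject for whom the survival status is not known". No search date is set, and no rule covers a subject whom the search shows to be alive.
- **Full withdrawal (6.6.1).** Where local rules permit, "publicly available data (death records) can be included after withdrawal of consent". Death records are the only example given.
- **Loss to follow-up (9.7.5).** After two failed contact attempts and a month without reply, "the subject will be considered lost to follow-up and no additional contact will be required".
- **Estimator (12.4).** "Kaplan-Meier estimates and 2-sided 95% confidence intervals will be generated for OS".
- **Use (12.5).** OS is summarised, and the efficacy endpoints are to be compared with historical controls.

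**The concern.** Kaplan-Meier estimation needs censoring that carries no information about the outcome. Take two subjects last contacted at month 4. One dies at month 10, the death is found in a record, and the subject is an event at month 10, at risk throughout. The other is alive at month 12 but, on the wording of 12.1, is censored at month 4. Both count as at risk up to month 4. After that, only the one who dies does. Censoring then depends on the outcome, and the risk sets for later deaths are too small.

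At stake is a one-directional error in a descriptive secondary endpoint. It matters most in the comparison with historical controls, whose follow-up may have been censored by another rule.

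**Working it through.** **The plan's own figure.** The plan states no OS figure. Its only computed design figure is the 19 subjects in 12.2, which reproduces: n0 = 1.96² × 0.5 × 0.5 / 0.10² = 96.04, and n = 96.04 / (1 + 95.04/24) = 19.36 (18.68 with a proportion of 0.3). The OS point does not depend on it.

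**Direction, without simulation.** Each death time multiplies the curve by 1 − d/n. If every death is captured, all d are as they would be with complete follow-up, but lost survivors leave n early. Each factor is therefore equal or smaller, and the curve cannot lie above the complete-data curve. Example: with 10 subjects truly at risk, 2 of them lost survivors, one death gives 7/8 = 0.875 instead of 9/10 = 0.900.

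**Size.** The documents give no loss rate, so these inputs are assumptions:
- Survival is exponential, with a median of 6.3 months (the retrospective chemorefractory cohort in 3.1.2, a different population), 12 months or 24 months.
- 5%, 10%, 20% or 30% of subjects are assigned a loss time, uniform over 12 months and independent of death. With a 12-month median, 3.6%, 7.2%, 14.4% and 21.7% are actually lost while alive.
- The cutoff is month 12, all deaths up to then are found, and survivors' dates are never updated.

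Kaplan-Meier OS at month 12 with deaths counted and survivors frozen at last contact (400,000 simulated subjects per cell):

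| True median (months) | True value | 5% | 10% | 20% | 30% |
|---|---|---|---|---|---|
| 6.3 | 0.267 | 0.261 | 0.255 | 0.243 | 0.227 |
| 12 | 0.500 | 0.492 | 0.484 | 0.469 | 0.451 |
| 24 | 0.707 | 0.702 | 0.696 | 0.682 | 0.668 |

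The shortfalls are 0.6 to 4.0, 0.8 to 4.9 and 0.5 to 3.9 points. In 4,000 simulated trials of 20 subjects, with a true value of 0.50, the means were 0.480, 0.470 and 0.449 at 10%, 20% and 30% loss, which is consistent.

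**Month 6 in the same runs.** The values are 0.514 to 0.506 (true 0.517), 0.705 to 0.694 (true 0.707) and 0.840 to 0.832 (true 0.841), a shortfall of 0.1 to 1.3 points. This small size depends on the later cutoff, because lost subjects who die between months 6 and 12 still count as at risk at month 6. If the cutoff were month 6 for everyone, with the same fractions assigned a loss time within 6 months, halving all times in the 24-month-median row gives a 12-month median and month-6 values of 0.702 to 0.668 against 0.707. That is 0.5 to 3.9 points.

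**Incomplete capture.** With half the records found, 20% loss and a 12-month median, the month-12 value is 0.484, not 0.469.

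**Symmetric rules.** Censoring searched survivors at the search or cutoff date returns the true month-12 value within 0.001. Censoring every lost subject at last contact and ignoring later deaths returns it within 0.002, but only because loss was assumed unrelated to death.

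**Scale.** With 20 subjects at S = 0.5, the 95% half-width is 1.96 × √(0.25/20) = 0.219, about 22 points.

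**The case against.** The strongest reply is that the asymmetry is partly inferred. Section 6.6.1 speaks of survival status, not only of deaths. Last contact is undefined and could be read to include a search or registry report of a living subject. Section 9.7.5 permits telephone calls to confirm survival, and 12.2 foresees long registry follow-up. Much of this stands: a reader might infer that OS will certainly be understated, and the documents do not support that. The searches are optional, and the bias needs both searches and lost or withdrawn subjects. What remains is that no passage moves the censoring date forward for a subject found alive, and that after full withdrawal only death records are named.

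A reader might also infer that lost subjects contribute no survival time. They do, up to last contact; only survivors' later time is missing.

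The sizes assume substantial loss and, in the main runs, full capture. This is a single-centre study of about 20 subjects, and study visits end 12 months from infusion, while OS starts at completion of radiotherapy given after the first 30 days. Month 12 of OS therefore lies beyond the scheduled visits. If capture is incomplete and lost subjects are sicker, an opposite bias could offset part of this one. Those limits stand.

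Section 12.5 defers bias-reducing data handling to a statistical analysis plan and a Trial Integrity Document. Those may settle the matter, but the text of 12.1 does not.

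Finally, a reader might infer from the duration-of-response (DOR) wording, under which a subject without progression or death "will be censored at their last evaluable disease assessment date and their response will be noted as ongoing", that ongoing responses will be overstated in the historical comparison. The time is still censored at the last assessment, 12.4 estimates cumulative incidence of relapse, and no planned estimate uses the label. It is a labelling note at most.

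**Conclusion.** The point holds conditionally and is minor. Applied as written, and only if record searches are done and some subjects are lost or withdraw, the OS rule makes censoring depend on outcome and pulls the Kaplan-Meier curve down. The month-12 and month-6 sizes rest on assumed loss rates, loss independent of death, exponential survival, full death capture and a 12-month cutoff; the month-6 figure would be larger with an earlier cutoff. Even the largest shortfall is well inside the sampling error with 20 subjects. The safety primary endpoint is untouched, and no OS test or threshold depends on the result. It is still worth correcting, because the error is systematic and whether it occurs should not turn on an optional, undated step.

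**What to change.** In 12.1, replace the OS censoring sentence with three rules:

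1. Subjects not known to have died are censored at the latest date on which any source (contact, record search or registry) shows them alive, not later than the data cutoff.
2. Any record search is run for all subjects of unknown status, on one common date.
3. Where only death records can be searched, as after full withdrawal, OS is censored at last contact in the main analysis and later deaths are left out. A sensitivity analysis includes them.

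The third rule is needed because the absence of a death record gives no date last known alive, so the first rule alone would leave the asymmetry in place for these subjects. It assumes that withdrawal is unrelated to prognosis, which is why the sensitivity analysis should be reported beside it.

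The cost is a few sentences, a small amount of search work that 6.6.1 allows but does not require, and possibly a few known deaths left out of the main estimate. Optionally, DOR listings could keep the ongoing label for responders still under follow-up; no estimate would change.

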12.2 Sample Size, Accrual Rate and Study Duration

In terms of number of patients we anticipate to enroll, 53 patients underwent axicel or tisacel therapy at MGH within the past year. With a modest 30% refractory disease rate, 16 patients would have refractory disease and may be eligible for radiation therapy to achieve disease control. For the next one year, given the increasing rate of patients being referred for CAR T cell therapy, we expect that 80 patients are expected to undergo axicel or tisacel therapy – as such, **we modestly anticipate enrolling 20 patients who are candidates for RT on this study.** In terms of sample size calculation, with a 95% confidence level and a confidence interval of 10, with 0.3 (refractory disease rate) * 80 patients = 24 eligible in the population, the required sample size is 19 patients. It is noted that this is a **pilot** study, where the primary objective is assessing safety and toxicity, within the limits of what a pilot study can establish. Typically recommended ranges for pilot study sample sizes tend to range from 10 – 30. The number 20 is based primarily on how many patients can be accrued within a year and how many patients there is funding for. We are most concerned about Grade 4 or higher toxicity within RT field. Patients will have many different anatomic sites in terms of radiation treatment. Inherently, while a sample size calculation can be done as an exercise, the validity of it is highly questionable given the multiple anatomic sites to which patients may receive RT and no published data of patients who undergo RT following CAR T cell therapy. Results from this pilot study will be used to design a larger study, and for that, sample size can be computed based on what safety and

toxicity-related events are seen in the pilot study. Univariate descriptive statistics with t-tests will be used to analyze pre- and post-RT QOL and toxicity data.

All subjects will be followed for survival for up to approximately 15 years after the last subject receives CAR T cell therapy, with data collected through the CIBMTR data registry starting at Month 24.

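### The 19-patient, ±10-point calculation depends on a finite-population correction to 24 local patients that does not apply; 20 patients give about ±22 to 23 points at worst, and the primary toxicity rate has no planned interval

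*Combined protocol and SAP*

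**What the plan says.** Section 12.2 forecasts 80 CAR T patients in the coming year, applies a 30% refractory rate, and obtains 24. It then states that "with a 95% confidence level and a confidence interval of 10", and with "24 eligible in the population, the required sample size is 19 patients". It gives no formula and no anticipated proportion.

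The same section qualifies this. It says of a sample size calculation that "the validity of it is highly questionable given the multiple anatomic sites to which patients may receive RT and no published data" exist, cites a customary pilot range of 10 to 30, and explains that "The number 20 is based primarily on how many patients can be accrued within a year and how many patients there is funding for". It also says that "Results from this pilot study will be used to design a larger study".

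The primary endpoint in section 12.1 is "Rate and severity of RT-related toxicity as per CTCAE v5.0 criteria during RT or within the first 30 days of completing RT". For safety, section 12.4 tabulates "Subject incidence rates of adverse events including all, serious, fatal, CTCAE version 5.0 Grade 3 or higher and treatment related AEs" over the whole conduct of the study and names no interval. The same section plans 95% intervals for objective response (exact), cumulative incidence of relapse, PFS and OS. The only other analysis named for toxicity, in section 12.2 and the synopsis, is "Univariate descriptive statistics with t-tests will be used to analyze pre- and post-RT QOL and toxicity data".

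**The concern.** Nineteen patients is far too few to estimate a mid-range proportion to within 10 points. The figure makes sense only if the 24 patients expected at one centre in one year are treated as the entire population, so that observing most of them leaves little uncertainty. The pilot is meant to inform treatment of later patients and the design of a larger study, and for that purpose 24 is not a population size. It is a forecast of accrual.

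At stake is what the reader believes 20 patients can show about the primary endpoint. The later study is to be sized from the toxicity seen here, so the real uncertainty should be on the page. The analysis section does not supply it either, since the primary rate is the one main result without a planned interval.

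**Working it through.** **Inputs.** From section 12.2: 95% confidence (z = 1.96), an interval of 10, N = 0.3 × 80 = 24, stated n = 19, planned n = 20. The anticipated proportion p is not stated. I assume p = 0.5 (worst case) and also show 0.3 and lower values.

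**Reproducing the 19.** Reading the 10 as a half-width e = 0.10:

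- Uncorrected: n0 = z² p(1 − p)/e². At p = 0.5, 3.8416 × 0.25/0.01 = 96.04, so 97 patients. At p = 0.3, 3.8416 × 0.21/0.01 = 80.67, so 81.
- Corrected for N = 24: n = n0/(1 + (n0 − 1)/N). At p = 0.5, 96.04/(1 + 95.04/24) = 19.36. At p = 0.3, 80.67/(1 + 79.67/24) = 18.68.

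Both corrected values round to the stated 19.

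**Other readings.**

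- Taking 10 as the full width (e = 0.05) gives 22.6 at p = 0.5 and 22.4 at p = 0.3 after correction. At p = 0.1 it gives 20.6, which is near 19 but also uses the correction.
- Without the correction and with e = 0.10, 19 requires an assumed rate of about 5%: 3.8416 × 0.0475/0.01 = 18.25. The text names no such rate, and this route gives the 24 no role.

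**Precision at n = 20, normal approximation.**

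- With the correction, p = 0.5: 1.96 × √(0.25/20 × 4/23) = 9.1 points.
- Without it, p = 0.5: 1.96 × √(0.25/20) = 21.9 points. At p = 0.3: 1.96 × √(0.21/20) = 20.1 points.
- Ratio at p = 0.5: 21.9/9.1 = 2.4.

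**Exact (Clopper-Pearson) 95% intervals at n = 20.** Half-width is half the distance between the limits.

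| Events | Interval (%) | Half-width (points) |
|---|---|---|
| 0 | 0 to 16.8 | 8.4 |
| 1 | 0.1 to 24.9 | 12.4 |
| 2 | 1.2 to 31.7 | 15.2 |
| 4 | 5.7 to 43.7 | 19.0 |
| 6 | 11.9 to 54.3 | 21.2 |
| 10 | 27.2 to 72.8 | 22.8 |

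The half-widths mirror above 10, so every count from 1 to 19 gives between 12.4 and 22.8 points. To hold the exact half-width to 10 points in the worst case takes 104 patients.

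**Grade 4 or higher.** Section 12.2 names this as the toxicity of most concern. With 0/20 the two-sided 95% upper limit is 1 − 0.025^(1/20) = 16.8%, and the one-sided 95% limit is 1 − 0.05^(1/20) = 13.9%. A true rate of 10% yields no events with probability 0.90^20 = 0.12, and a true rate of 5% with probability 0.95^20 = 0.36.

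**The primary analysis.** Section 12.1 fixes a window from the start of RT to 30 days after its completion. The section 12.4 tables run over the whole study and carry no interval. A before-and-after t-test cannot estimate the RT-related rate, because an event attributed to RT cannot occur before RT.

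**The case against.** The protocol is candid about this calculation. It calls the validity of such an exercise highly questionable, says 20 comes primarily from accrual and funding, and cites a usual range for pilots. No test, success threshold or stopping rule uses 19 or ±10, so nothing later in the plan fails. The correction is inferred rather than named, and an uncorrected 5% rate also gives 19. At 0/20 the half-width is 8.4 points, inside the stated 10. The t-tests may be meant for paired survey scores, which the schedule does collect before and after RT. An exact interval can also be computed by anyone from a count out of 20.

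Much of this limits the consequence: the sample size stands, and paired comparisons of survey scores are untouched. It does not rescue the figure. The stated doubts concern mixed anatomic sites and missing published data, not the closed population of 24, and the 19 and the 10 remain in the text. The 5% route leaves the 24 unexplained, and even 1/20 has an exact half-width of 12.4. For 0/20 the useful figure is the upper limit of 16.8%. The missing interval, taken alone, would be closer to missing detail than to error. It belongs here because section 12.4 already gives a secondary endpoint, objective response, an exact interval.

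**Conclusion.** The concern holds. The arithmetic behind 19 can be reproduced, but it answers a question about a closed group of 24 patients, which is not the question the pilot asks. For inference to later patients, 20 subjects give a 95% half-width of 21.9 points (normal) or 22.8 points (exact) at a rate of 50%. That is about 2.4 times the ±9.1 points that the corrected formula would imply at that size. A clean result for grade 4 or higher toxicity excludes only rates above 16.8%.

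This rests on three readings: the 10 is a half-width in percentage points, the unnamed proportion is 0.5 or 0.3, and the target is future patients. The first two are the ones that return 19 and give the 24 a role. The third follows from the stated plan for a larger study. The point should be fixed because a stated precision is wrong by a factor of about two and the primary endpoint's analysis is incomplete. It does not call the number 20 into question.

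**What to change.** - **Section 12.2:** keep 20 on its accrual and funding basis. Delete the 19-patient, ±10 calculation and state exact binomial precision at n = 20 instead.
- **Grade 4 or higher RT-related toxicity:** quote 0/20 with its upper limit of 16.8%. Add that sections 7.4.4 and 12.3 pause enrolment or stop the study at any such event, so fixed-n intervals for 1/20 or more would not describe a trial run as planned.
- **Lower-grade toxicity:** quote a range, for example 2/20 (1.2 to 31.7%), 4/20 (5.7 to 43.7%), 6/20 (11.9 to 54.3%) and 10/20 (27.2 to 72.8%).
- **Section 12.4:** add a table of RT-related toxicity by worst grade, restricted to the section 12.1 window, with exact two-sided 95% intervals.
- **Section 12.2 and the synopsis:** state that the before-and-after t-tests are not used for the RT-related toxicity rate.

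The cost is wording in these sections and a less favourable statement of precision. No patients, visits or data are added.
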